Collected data included patient demographics (age, sex, growth parameters), procedure indication, patient's overall health status based on the American Society of Anesthesiologists (ASA) classification, endoscopy-related characteristics (duration, trainee vs faculty endoscopist and complications) and anesthesia-related parameters (duration, medication dosing, and complications). Vital signs, including EtCO₂, heart rate, respiratory rate, oxygen saturation, and blood pressure were monitored and automatically recorded continuously throughout the procedure, according to the anesthesia protocol. EtCO₂ was monitored and continuously sampled by nasal prong or via capnography for intubated patients.

Outcome Measures

Patient discomfort was assessed using 3 scales:

1. Face, Legs, Activity, Cry, and Ability to be Consoled (FLACC) behavioral assessment score
2. Global Parent Perception of Pain (PPP) scale
3. FACES scale; for neurodevelopmentally appropriate children 5 years and older.

Pain

FLACC at baseline, within 15 minutes of return to recovery area, when awake. FLACC scores categorized as no pain, mild pain, moderate to severe pain, very severe pain or worst pain ever

PPP at baseline, when awake and 4 hours post discharge. PPP scores categorized as no pain, mild pain, moderate to severe pain, very severe pain or worst pain ever

VAS at baseline, when awake and 4 hours post discharge. VAS scores categorized as no pain, mild pain, moderate to severe pain, very severe pain or worst pain ever

Abdominal girth at baseline, after procedure, at discharge, and 4 hours post discharge

Endoscopist assessment

Perceived ease of inflation: easy or average, mild difficulty, very difficult

Perceived patient discomfort: comfortable or average discomfort, above average discomfort

Endoscopist guess of inflation gas

Abdominal girth was measured by the same nurse at the level of the umbilicus before the procedure, immediately upon arrival in the recovery area after the procedure, and again just before discharge. Patients were sent home with a tape measure and a postage-prepaid response card on which they recorded the abdominal girth four hours after completion of the procedure. Parents were also asked to indicate if the patient had experienced belching, bloating or flatulence.

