#### STATISTICAL ANALYSIS PLAN

Cohort demographics were analyzed using descriptive statistics. Continuous variables were summarized using the mean, and standard deviation (SD) or median and interquartile range (IQR) and compared using the Student t-test for normally-distributed data and the Wilcoxon rank-sum test for data with skewed distribution. Categorical variables were summarized using counts and frequency as a percentage and compared using Chi-Square test or Fisher's exact test. A p-value  $<0.05$  was considered statistically significant. Statistical analysis was performed with SAS 9 statistical software (SAS Institute, Cary, NC).

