#### Power calculation

The number of subjects enrolled was based on other studies, with the assumption that up to 20% of patients in the air insufflation group would report some degree of abdominal pain after endoscopy. We estimated that the frequency of reported abdominal pain in the CO2 group would be one-fourth of that (5%) seen in the air group. To accomplish this, a minimum total of 150 subjects would be needed (significance level of 5%, power of 80%) so we aimed to recruit a total of 180 patients (enrollment ratio of 1).

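### Pain is scored at baseline, but the SAP gives that score no role in comparing the arms; if raw post-procedure pain is compared, pain already present may dilute the difference.

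*Protocol*

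**What the plan says.** Under Outcome Measures (Pain), the protocol gives FLACC, PPP and VAS a baseline assessment and later ones. For the parent scale the schedule is "PPP at baseline, when awake and 4 hours post discharge". Each score is then placed in ordered categories starting at no pain.

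The protocol's exclusions (Subjects and Randomization) cover the need for an interpreter and significant chronic lung disease. Pain at entry is not among them. Eligible procedures are diagnostic or therapeutic and include exchange of an existing PEG tube.

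The SAP's analysis paragraph is generic: "Categorical variables were summarized using counts and frequency as a percentage", with chi-square or Fisher tests between arms, and t-tests or rank-sum tests for continuous data. It names no pain scale, time point, change score or baseline covariate. Part of the SAP was not in the text available here.

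The only pain endpoint with a stated form is in the SAP's Power calculation, which assumes that "up to 20% of patients in the air insufflation group would report some degree of abdominal pain after endoscopy" and that "the frequency of reported abdominal pain in the CO2 group would be one-fourth of that (5%) seen in the air group".

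**The concern.** Children come to endoscopy because of a gastrointestinal problem or a feeding tube, so some may well have pain on arrival. The sizing endpoint counts any child who "would report some degree of abdominal pain after endoscopy". A child with mild pain before and the same mild pain afterwards meets that description in either arm, although the gas did not cause it.

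Such children add the same block of events to both arms. The absolute difference shrinks, the pooled event rate moves towards 50%, and the test loses power. A null result could then not be told apart from a diluted one. The information needed to separate the two is already collected, but no available text uses it.

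**Working it through.** **Inputs from the SAP, Power calculation:** air 20%, CO2 5%, significance level 5%, power 80%, minimum total 150 (75 per arm), target 180 (90 per arm), allocation 1:1. Sidedness is not stated; two-sided is assumed, because a one-sided calculation gives 120 in total (144 with continuity correction).

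**Step 1: reproduce the plan's figure.** With pooled variance and no continuity correction, the mean rate is (0.20 + 0.05)/2 = 0.125 and

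n per arm = [1.960·√(2·0.125·0.875) + 0.842·√(0.20·0.80 + 0.05·0.95)]² / 0.15² = (0.917 + 0.383)² / 0.0225 ≈ 75.1.

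Rounded up, this is 76 per arm, or 152 in total, against the stated 150. Power at 75 per arm is 79.9%, so the stated size is reproduced.

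**Step 2: add persisting baseline pain.** Let b be the share of children whose baseline pain is still present afterwards whichever gas is used. The documents give no value for b, so a range is shown. Suppose that 20% and 5% are rates of new pain among the remaining children. Then

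- air: b + (1−b)·0.20
- CO2: b + (1−b)·0.05
- difference: (1−b)·0.15

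Power below is by exact enumeration of the two binomial outcomes, using a two-sided 5% uncorrected chi-square test.

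| b | Air | CO2 | Difference (points) | Power, 75 per arm | Power, 90 per arm |
|---|---|---|---|---|---|
| 0 | 20.0% | 5.0% | 15.0 | 82.7% | 89.0% |
| 2.5% | 22.0% | 7.4% | 14.6 | 74% | 81% |
| 5% | 24.0% | 9.8% | 14.3 | 66.3% | 73.5% |
| 10% | 28.0% | 14.5% | 13.5 | 53.0% | 60.4% |
| 20% | 36.0% | 24.0% | 12.0 | 35.7% | 42.0% |
| 30% | 44.0% | 33.5% | 10.5 | 27.2% | 31.2% |

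The normal approximation gives nearly the same at b=10% (52.5% and 60.2%) and b=20% (36.0% and 41.9%).

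Here b counts persisting pain only. If 20% of children arrive in pain and half of them still have it afterwards, the b=10% row applies.

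**Step 3: what using baseline could recover under the same assumption.** Children with persisting pain carry no information about the gas in this model, so the informative comparison is among the rest, 75(1−b) or 90(1−b) per arm at 20% against 5%. By the normal approximation, power is 75.6% and 82.9% at b=10%, and 70.5% and 78.3% at b=20%. These figures indicate what separating children by baseline pain can recover. They are not the power of a particular regression model.

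**Step 4: the other reading of 20% and 5%.** If these rates already include all pain reported after endoscopy, nothing is added on top and the planned power stands. Persisting pain then cannot exceed 5% in the CO2 arm or, by randomisation, about 5% in the air arm. Using baseline can still help: if 2 points of each rate were persisting pain, new pain would be 18% against 3%, with exact power at 75 per arm of 89.8% instead of 82.7%.

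**The case against.** Three objections have weight.

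First, a reader might infer that the SAP compares only post-procedure pain. The documents do not say so. The listed tests could equally be applied to a change score or to new pain, the Power calculation is a sizing assumption and not an analysis rule, and part of the SAP was not available. What stands is narrower: no available text gives the baseline score a role.

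Second, a reader might infer that the comparison is invalid, or that the gas effect is bound to be hidden. Randomisation balances baseline pain in expectation. An unadjusted test keeps its type I error and validly estimates the effect on any pain after the procedure. The possible harm is dilution and lost precision.

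Third, the losses in the table depend on reading 20% and 5% as new pain. The SAP's wording, taken literally, covers all pain reported after endoscopy. On that reading the rows with b of 10% or more contradict the plan's own CO2 rate, and the power loss disappears. Even on the new-pain reading, power at 90 per arm is still about 81% when b is 2.5%.

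All three limit the size of the point. None of them gives a reason to leave a collected baseline score unused.

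**Conclusion.** The point holds as a gap in the analysis plan with an inexpensive remedy. Baseline pain is collected on every scale that has a schedule, the available SAP text does not use it, and the one defined endpoint would count pain that was there beforehand.

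The consequence is conditional. If raw post-procedure pain is compared and 20% and 5% mean new pain, persisting baseline pain in 5% of children is enough to take power below 80% at the full 180 patients, and 10% takes it to about 60%. These figures assume that this pain persists whichever gas is used, and b itself is unknown. If 20% and 5% already cover all pain, the planned power is unaffected and the gain from using baseline is in precision only. The documents do not settle which reading was meant.

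**What to change.** In the SAP, name the pain scale and time point for the comparison. Compare post-procedure pain between arms with the patient's baseline score on the same scale as a covariate, using ordinal regression for the categories or logistic regression for any pain. Tabulate baseline pain by arm. Report two supporting results: the unadjusted proportion with pain, and the proportion with new or worsened pain. State whether 20% and 5% refer to new pain or to all pain.

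The cost is mainly SAP wording, since the scores are already collected. Some details need care:

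- A rule is needed for patients with a missing baseline score.
- New or worsened pain should remain a supporting result. On a coarse ordered scale it has a ceiling, it misses worsening within a category, and it is not the quantity the trial was sized on.
- Events may be few: 5% of 75 to 90 children is about 4 in the CO2 arm. The baseline term should be kept simple, with a stated fallback if the model does not fit, such as a test stratified by baseline pain (yes or no).
- The SAP is written in the past tense. If pain results by arm have already been seen, the adjusted analysis should be labelled as added afterwards.

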Cover page

Title: Safety and Efficacy of CO2 for Endoscopy

NCT 03287687

1/1/2020

Study Protocol:

The current literature in pediatric endoscopy does not include evidence on effectiveness and safety of CO2 insufflation in procedures besides colonoscopy and does not include children in the younger age range. Esophagogastroduodenoscopy procedures (EGDs) are much more commonly performed procedures in children so it is important to assess these clinical scenarios before adopting CO2 insufflation as the main mode of practice.

Our study aimed to address these knowledge gaps by enrolling younger children, including infants, and a wide variety of endoscopic procedures, including EGDs and percutaneous endoscopic gastrostomy (PEG) tube placement.

Study Design

This is a double-blinded, prospective, randomized study comparing CO₂ and air for insufflation during endoscopic procedures in pediatric patients performed in the Pediatric Endoscopy Unit at the University of Iowa Children's Hospital. The study was approved by the Institutional Review Board (IRB) at the University of Iowa

Subjects and Randomization

Patients aged 6 months to 21 years undergoing diagnostic or therapeutic endoscopic procedures were offered participation. These procedures included EGD, colonoscopy, PEG tube placement, and endoscopic PEG tube exchange. Exclusion criteria included non-English-speaking families needing an interpreter and patients with significant chronic lung disease, such as bronchopulmonary dysplasia, severe asthma, or cystic fibrosis. Consents and assents were obtained prior to enrollment.

Both the patient and endoscopist were blinded to the arm of study. Randomization was done by the procedure suite nurse using a sealed envelope system. To maintain allocation concealment, the nurse set up the equipment to deliver CO₂ or air then covered the relevant equipment settings

to assure complete blinding of the endoscopist and others in the room. The equipment was adjusted to deliver CO₂ or air at a similar flow rate.

Data Collection

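### The SAP does not say that baseline abdominal girth is used: baseline-adjusted ANCOVA would cost almost nothing, gaining much precision over raw girth but little over change from baseline

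*Protocol*

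**What the plan says.** The Protocol, under Outcome Measures, lists "Abdominal girth at baseline, after procedure, at discharge, and 4 hours post discharge". The same section adds that "Abdominal girth was measured by the same nurse at the level of the umbilicus before the procedure", with repeat measurements on arrival in recovery and just before discharge. The last value comes from the family: "Patients were sent home with a tape measure and a postage-prepaid response card on which they recorded the abdominal girth".

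The Protocol, under Subjects and Randomization, sets a very wide age range: "Patients aged 6 months to 21 years undergoing diagnostic or therapeutic endoscopic procedures were offered participation".

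The SAP, under Statistical Analysis Plan, gives one general rule for continuous variables. They are summarised and "compared using the Student t-test for normally-distributed data and the Wilcoxon rank-sum test for data with skewed distribution". The supplied text does not name girth and mentions no change score, covariate, regression or repeated-measures model. One part of the SAP was not in the text available for this review, so these statements cover the supplied text only.

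The SAP, under Power calculation, bases the sample size on pain. It assumes that "up to 20% of patients in the air insufflation group would report some degree of abdominal pain after endoscopy", against 5% with CO2.

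**The concern.** Girth is measured to detect distension from insufflated gas. Between an infant and a 21-year-old, however, most of the variation in girth is likely to be body size. The baseline value carries nearly all of that information and has already been collected.

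The SAP rule fits two analyses: a two-sample test on raw post-procedure girth, or the same test on change from baseline. The first puts the body-size spread into the error term, widens the confidence interval and leaves the result exposed to chance imbalance in body size between arms. A null result could then be misread as evidence of no difference in distension. The second removes most of that spread. With the choice unstated, a reader cannot tell which precision to expect, and the choice could be made after results are seen.

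**Working it through.** **The plan's own figure.** Inputs from the SAP, Power calculation: 20% vs 5%, significance level 5% (taken as two-sided), power 80%, ratio 1. The two-proportion formula with pooled variance and no continuity correction gives 76 per arm, 152 in total; 75 per arm gives 79.9% power. This agrees with the statement that "a minimum total of 150 subjects would be needed". The sample size is not in dispute.

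**Inputs for girth.** From the SAP: 90 per arm (target 180 at ratio 1) and 75 per arm (minimum 150). The documents give no girth SD, no baseline-to-follow-up correlation r and no target difference. Assumed for illustration: SD 15 cm (range 8 to 20) and r 0.95 (range 0.80 to 0.98).

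**Formulas.** Difference detectable with 80% power at two-sided 5%:

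- raw girth: 2.8016 × SD × √(2/n)
- change from baseline, equal SDs: raw × √(2(1 − r))
- ANCOVA on baseline: raw × √(1 − r²)

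**At SD 15 and r 0.95:**

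- n = 90 per arm: raw 2.8016 × 15 × √(2/90) = 6.26 cm; change 6.26 × 0.316 = 1.98 cm; ANCOVA 6.26 × 0.312 = 1.96 cm.
- n = 75 per arm: 6.86, 2.17 and 2.14 cm, each √(90/75) = 1.095 times the value at 90.
- 95% CI half-widths at 90 per arm: 4.38, 1.39 and 1.37 cm.

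**Over the range of r (SD 15, 90 per arm):**

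| r | Raw (cm) | Change (cm) | ANCOVA (cm) | Raw ÷ ANCOVA | Change ÷ ANCOVA |
|---|---|---|---|---|---|
| 0.80 | 6.26 | 3.96 | 3.76 | 1.7 | 1.05 |
| 0.90 | 6.26 | 2.80 | 2.73 | 2.3 | 1.03 |
| 0.95 | 6.26 | 1.98 | 1.96 | 3.2 | 1.01 |
| 0.98 | 6.26 | 1.25 | 1.25 | 5.0 | 1.01 |

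Neither ratio depends on the SD when baseline and follow-up SDs are equal: the first is 1/√(1 − r²), the second √(2/(1 + r)). The values in cm scale with the SD; raw runs from 3.3 cm (SD 8) to 8.4 cm (SD 20) at 90 per arm.

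**Unequal SDs.** With follow-up SD 15 and baseline SD 12, the variance of change at r 0.95 is 144 + 225 − 2 × 0.95 × 12 × 15 = 27. With baseline SD 16.5 it is 272.25 + 225 − 470.25 = 27. Either way the detectable difference on change is 2.8016 × √27 × √(2/90) = 2.17 cm, about 11% above ANCOVA (2.17/1.96).

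**Wilcoxon.** On normal data the rank test multiplies these figures by √(π/3) = 1.023: raw 6.41 cm and change 2.03 cm at 90 per arm.

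**Simulation.** With 4,000 runs, r 0.95, 90 per arm and a true difference of 1.955 cm, power was 14% for raw girth, 78% for change and 79% for ANCOVA.

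All figures assume complete data, a common additive effect in cm and equal residual variance across ages.

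**The case against.** The strongest objection is that the SAP does not commit to testing raw girth. Its sentence covers continuous variables in general, and a t-test or Wilcoxon test on change from baseline satisfies it fully. Listing a baseline taken by the same nurse fits within-patient change at least as well. On that reading ANCOVA gains little: 1.96 against 1.98 cm in the illustration. This stands. A reader might infer that the plan tests raw girth and has thrown away two-thirds of its precision; the documents show only silence on the point. The 6.3 against 2.0 cm contrast is the worst case.

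Three further points stand:

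- The size of the loss rests on an assumed SD and r. Dominance by body size is a reasonable inference from the age range, not something the documents report.
- The 4-hour value is taken by families, so r may be lower there and the gain smaller. Its timing is also given two ways in Outcome Measures: the list counts from discharge, the narrative from the end of the procedure.
- A constant effect in cm may not hold from infants to adults, so the analysis scale needs thought.

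None of this removes the point. ANCOVA on baseline is far more precise than raw girth when r is high. Apart from a trivial degree-of-freedom cost it is never less precise than change, and it needs no new data.

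**Conclusion.** The point holds as a free improvement to an outcome that does not set the sample size. The supplied SAP text does not say how baseline girth is used.

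If raw girth is tested, the detectable difference is 1.7 to 5.0 times that of ANCOVA for r from 0.80 to 0.98 (6.3 against 2.0 cm at the assumed SD 15 cm, r 0.95 and 90 per arm). If change is tested, the loss is about 5% at r 0.80 and about 1% at r 0.95 with equal SDs, and somewhat larger if the SDs differ.

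Two stronger readings are not supported. The first is that a raw comparison would be biased: randomisation keeps it unbiased with complete data, and the cost is precision. Non-return of cards could bias the 4-hour comparison, but under any of these analyses. The second is that the trial is too small: the sample size rests on pain and reproduces. The documents do not rank their outcomes; girth's supporting role is inferred from the power calculation.

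**What to change.** Add to the SAP:

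- Analyse girth at each post-procedure time by ANCOVA with treatment and baseline girth. Report the adjusted treatment estimate with a 95% CI for every time point, whatever the result. A stated change-from-baseline test would recover nearly all of the gain.
- Fix the scale without reference to treatment results. Report a difference in cm if girth is analysed untransformed, or a ratio of geometric means if log girth is used. If residuals are clearly skewed, use a rank-based or robust analysis that still adjusts for baseline.
- For the home measurement, first reconcile the two descriptions of its timing. Then report card returns by arm, and note that the precision gain may be smaller because families take that value.
- The SAP is written in the past tense. If results are already known, label the analysis as not prespecified.

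The cost is a few sentences in the SAP and a few lines of SAS on data already collected. No extra patients, visits or measurements are needed, and the sample size does not change.

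### The 4-hour girth is taken at home by the family while all earlier girths are taken by a nurse, which adds noise, not bias, to the arm comparison; a paired family reading at baseline would recover much of the lost precision

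*Protocol*

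**What the plan says.** All girth provisions are in the Protocol under Outcome Measures.

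- **In-unit readings.** "Abdominal girth was measured by the same nurse at the level of the umbilicus before the procedure", then "immediately upon arrival in the recovery area after the procedure, and again just before discharge". The natural reading is one nurse per patient, not one nurse for the whole trial.
- **Home reading.** "Patients were sent home with a tape measure and a postage-prepaid response card on which they recorded the abdominal girth". Because enrolment covers "Patients aged 6 months to 21 years", a carer must take this reading for at least the youngest children.
- **Schedule.** The list gives "Abdominal girth at baseline, after procedure, at discharge, and 4 hours post discharge", while the narrative times the home reading "four hours after completion of the procedure". These two anchors differ and need to be reconciled, apart from the present point.
- **Blinding.** "Both the patient and endoscopist were blinded to the arm of study".
- **Analysis.** The SAP has no girth-specific method. Continuous variables are "compared using the Student t-test for normally-distributed data and the Wilcoxon rank-sum test for data with skewed distribution". It does not say whether girth is compared raw, as a change, or adjusted for baseline.

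The documents describe no family reading before the patient goes home, and nothing that links home readings to nurse readings.

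**The concern.** Over this age range, raw girth reflects body size far more than insufflated gas. A useful 4-hour comparison must therefore use each patient's own earlier reading. Every earlier reading is the nurse's, so the family's habits (tape level, tension, posture, clothing) do not cancel when the 4-hour value is set against it.

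Two things are at stake. The arm comparison on the only post-discharge girth is less precise than it could be. And within an arm, a fall or rise between discharge and 4 hours mixes true deflation with a change of measurer.

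**Working it through.** **Plan's own figures.** The documents give no number for girth. The one sample-size figure concerns pain (20% versus 5%, 5% significance, 80% power, minimum 150 in total). With a two-sided test, pooled variance and no continuity correction:

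n per arm = [1.96·√(2·0.125·0.875) + 0.8416·√(0.2·0.8 + 0.05·0.95)]² / 0.15² = 75.1, so 76 per arm and 152 in total.

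That reproduces 150 closely. The girth point does not touch it.

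**Assumptions for girth (none is in the documents).** True-change SD 1.5 cm; error SD of a single reading 1 cm; family-minus-nurse technique SD s = 1, 2 or 3 cm; 60 returned cards per arm; body size varying freely. Half-width = 1.96·√(2V/60), where V is the residual variance.

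**1. Within-arm reading.** Suppose true mean changes of −1.00 cm (air) and −1.75 cm (CO2), and a common home-minus-nurse shift of +2 cm. The observed means become +1.00 and +0.25 cm, so deflation looks like distension. The arm difference is −0.75 cm either way.

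**2. Present design, nurse reference only.** V = 1.5² + s² + 1 + 1 = 4.25 + s².

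**3. Nurse and family baselines both as covariates, technique fully carried over.** The best weighting of the two baselines predicts the patient's girth as that family would measure it, with error variance (s² + 1)/(s² + 2). So V = 1.5² + 1 + (s² + 1)/(s² + 2).

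**4. The same, with half the technique variance carried over.** The two baselines get equal weight. V = 1.5² + 1 + (s²/2 + 1)/2 + s²/2.

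**5. Paired reading at discharge, with the family-minus-nurse difference and the nurse baseline as covariates, full carry-over.** V = 4.25 + 2s²/(s² + 2).

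| s (cm) | Step 2: V, half-width | Step 3: V, half-width | Step 4: V, half-width | Step 5: V, half-width |
|---|---|---|---|---|
| 1 | 5.25, 0.82 | 3.92, 0.71 | 4.50, 0.76 | 4.92, 0.79 |
| 2 | 8.25, 1.03 | 4.08, 0.72 | 6.75, 0.93 | 5.58, 0.85 |
| 3 | 13.25, 1.30 | 4.16, 0.73 | 10.50, 1.16 | 5.89, 0.87 |

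Simulated trials of the same model agree with the closed forms to within about 0.03 cm (for step 3 at s = 2, 0.73 to 0.75 cm).

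**6. Why a discharge reading alone fails as the covariate.** Assume residual distension at discharge of 2.0 cm (air) and 0.5 cm (CO2), and at 4 hours of 0.75 and 0 cm. The true 4-hour effect is −0.75 cm. Because body size dominates, the covariate slope is close to 1, and the adjusted difference is about −0.75 − 1·(0.5 − 2.0) = +0.75 cm. Simulation gives +0.72 to +0.75 cm. The sign reverses. In step 5 the true girth cancels from the family-minus-nurse difference, so the gas effect is not adjusted away.

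**The case against.** The case for leaving the plan alone has several parts.

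- **Every girth input is assumed.** This stands. The benefit runs from small (0.82 to 0.71 cm at s = 1, full carry-over) to large (1.30 to 0.73 cm at s = 3), and the documents cannot say where the trial lies.
- **A reading taken beside the nurse may not resemble one taken alone at home.** This stands in part. With half carry-over the half-width at s = 2 falls only to 0.93 cm, but that is still a gain.
- **Subtracting a calibration outright can make things worse.** Correct: a fixed four-reading correction has V = 2.25 + 4 = 6.25, against 5.25 now at s = 1. Estimating the coefficient in ANCOVA avoids this (4.92).
- **The SAP plans no within-arm trend.** Correct. A reader might infer that the plan joins the home value to the nurse series and interprets the result as gas clearing. It only lists the time points and specifies two-group tests. The within-arm point is a caution for reporting, not an error in a planned analysis.
- **Home measurement is an ordinary compromise after discharge, and girth does not set the sample size.** Both are true, and they limit the weight of the point.

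A reader might also infer that the change of measurer biases CO2 against air. The documents do not support that. Allocation is random, the trial is described as double-blinded, and patients and those in the procedure room are kept unaware of the gas. Bias would need card return or unblinding to differ by arm, and nothing in the documents shows this. Nor can one infer that families received no measuring instructions, since the text of the response card is not in the documents.

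**Conclusion.** The point holds as a loss of precision on a supporting outcome. The change of measurer at 4 hours is plain on the text. Its expected effect on the arm contrast is noise common to both arms, and the three nurse readings are unaffected. The discharge-to-4-hour change within an arm is not interpretable as deflation.

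Under the stated assumptions the avoidable widening at technique SD 2 cm is about 0.3 cm of half-width with full carry-over (1.03 against 0.72–0.75 cm) and 0.1 cm with half (1.03 against 0.93 cm). At SD 1 cm it is about 0.1 cm or less. The size is uncertain because every SD, the return rate and the degree of carry-over are assumptions. This is a worthwhile low-cost improvement. It is not a threat to the trial's main comparison.

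**What to change.** 1. Before the procedure, have the family take one reading with the take-home tape beside the nurse's baseline reading, and record both.
2. State in the SAP that the arms are compared on 4-hour girth by ANCOVA, with the nurse baseline and the family baseline as covariates.
3. Do not use a discharge reading alone as the covariate. If the paired reading can only be taken at discharge, enter the family-minus-nurse difference as a calibration covariate together with the nurse baseline.
4. Report 4-hour girth as a between-arm comparison, and state the change of measurer as a limitation.

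The cost is about one minute per patient, one data field and a short wording change in each document; the family also gets a practice reading. If data collection is already complete, as the documents' past tense may suggest, only the analysis part remains: ANCOVA on the nurse baseline, plus item 4. That keeps the comparison unbiased but does not recover the lost precision.

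### Belching, bloating and flatulence have no stated baseline, so symptoms a child already had cannot be told apart from symptoms after insufflation; this costs power but does not favour either arm

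*Protocol*

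**What the plan says.** The Outcome Measures section of the protocol sets a schedule for each pain measure it times and for girth, and every schedule starts at baseline:

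- FLACC: "FLACC at baseline, within 15 minutes of return to recovery area, when awake"
- PPP: "PPP at baseline, when awake and 4 hours post discharge"
- VAS: "VAS at baseline, when awake and 4 hours post discharge"
- Girth: "Abdominal girth at baseline, after procedure, at discharge, and 4 hours post discharge"

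Gas symptoms are not in that timed list. They appear in one sentence at the end of the section: "Parents were also asked to indicate if the patient had experienced belching, bloating or flatulence". The sentence before it describes a "postage-prepaid response card on which they recorded the abdominal girth four hours after completion of the procedure", which suggests, without saying so, that the symptom question was on the same card.

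For analysis, the SAP's general paragraph covers these items: "Categorical variables were summarized using counts and frequency as a percentage and compared using Chi-Square test or Fisher's exact test". It describes no adjustment for baseline and no rule for separating new symptoms from existing ones. The SAP's power calculation rests on abdominal pain, assuming that "up to 20% of patients in the air insufflation group would report some degree of abdominal pain after endoscopy", with 5% on CO2. It does not mention gas symptoms.

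**The concern.** The participants are children having diagnostic or therapeutic endoscopy, including colonoscopy and PEG procedures. It is plausible that some already belch, bloat or pass gas, although the documents give no rate. A parent of such a child can truthfully answer yes after either gas. Without a matching answer from before the procedure, the analyst cannot tell that yes from one caused by insufflation. Procedure indication is collected and would allow a rough subgroup, but it does not record which children had which symptom.

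At stake is the reading of the only gas symptoms the trial collects. Children who would answer yes regardless raise the rate in both arms and shrink the difference between them. A real benefit of CO2 on these symptoms could then appear as no difference. The protocol takes a baseline for pain and girth, so the omission departs from its own practice.

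**Working it through.** **Inputs from the documents.** SAP, Power calculation: pain 20% on air and 5% on CO2, significance level 5%, power 80%, minimum 150 in total, target 180 at 1:1, hence 180/2 = 90 per arm.

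**The plan's own figure.** The pooled-variance two-proportion formula, two-sided and without continuity correction, gives 76 per arm, 152 in total. At 75 per arm, power is 79.9%. The stated 150 is reproduced to within 2 patients and is not in dispute. The same method is used below.

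**Assumptions.** The documents give no rate for belching, bloating or flatulence. For illustration, let new symptoms occur in p = 40% on air and 20% on CO2. Let a share b of children in each arm already have the symptom and answer yes regardless of gas.

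**Formulas.**

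- Observed rate: p′ = b + (1 − b)p. The difference shrinks by the factor (1 − b).
- Power = Φ[(d − 1.96·se₀)/se₁], where d = p₁′ − p₂′, se₀ = √(2·p̄(1 − p̄)/n), se₁ = √([p₁′(1 − p₁′) + p₂′(1 − p₂′)]/n), and p̄ is the mean of the two observed rates.
- Restricted analysis: 90(1 − b) children per arm who are symptom-free at baseline, compared at 40% vs 20%.

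**Worked line, b = 20%, n = 90.** p₁′ = 0.20 + 0.80 × 0.40 = 0.52. p₂′ = 0.20 + 0.80 × 0.20 = 0.36. d = 0.16 and p̄ = 0.44. se₀ = √(2 × 0.44 × 0.56/90) = 0.0740. se₁ = √((0.2496 + 0.2304)/90) = 0.0730. Power = Φ[(0.16 − 0.1450)/0.0730] = Φ(0.205) = 58%.

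| Background b | Observed, air vs CO2 | Power, all children, 90 per arm | Symptom-free at baseline, per arm | Power, restricted |
|---|---|---|---|---|
| 0% | 40% vs 20% | 84% | 90 | 84% |
| 5% | 43% vs 24% | 78% | 85.5 | 82% |
| 10% | 46% vs 28% | 71% | 81 | 80% |
| 20% | 52% vs 36% | 58% | 72 | 75% |
| 30% | 58% vs 44% | 47% | 63 | 69% |

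**Sensitivity to sample size.** At the stated minimum of 75 per arm, power is 77% with no background and 63%, 51% and 40% at 10%, 20% and 30%. The restricted analysis gives 72%, 67% and 61%.

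**Sensitivity to the rates.** Borrow the SAP's pain rates, 20% vs 5%, as new-symptom rates at 90 per arm. Power is 86.7% with no background. At 10%, 20% and 30% background it is 60.2%, 41.9% and 30.3%; the restricted analysis gives 82.9%, 78.3% and 72.6%.

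**Limit of the restricted column.** In this model a child symptomatic at baseline always answers yes and so carries no information about the gas. Stratifying by the baseline answer would then amount to the restricted analysis. Where some of those children would answer no, the two differ, and that case was not computed.

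**The case against.** The strongest reply has four parts.

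- **A window is implied.** The symptom sentence follows directly on the take-home card and is joined to it by the word also, so its natural reading is symptoms after the procedure. A reader might infer that parents were asked about any time in the child's life. The documents do not support that: the past tense is the protocol's narrative style, and the card itself is not reproduced. This part stands. What remains is that the window is not stated, and that the card's time point is four hours after the procedure in the narrative but four hours after discharge in the outcome list. A clear window would still not separate usual flatulence from new flatulence.
- **Randomization protects the comparison.** Earlier symptoms should balance on average, and the protocol states that patient, endoscopist and anesthesiologist were blinded. A reader might infer bias towards one gas; there is no ground for that. Randomization does not prevent dilution, however.
- **The item is ancillary.** The sample size rests on pain, the timed pain measures have baselines, and girth, an objective reading of distension, has a baseline and three later readings. This stands and limits the weight of the point.
- **The rates are assumed.** This also stands. The relevant background is only what would produce a yes in the short period after the procedure whatever the gas, and the documents give no basis for any value. At 5% the loss is small, from 84% to 78%.

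**Conclusion.** The concern holds in a limited form. No baseline is stated for the three gas symptoms, and the planned analysis is unadjusted, so existing and new symptoms cannot be separated. The consequence is dilution and lost power on an ancillary outcome. The trial's pain and girth comparisons are not affected.

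Under the assumed 40% vs 20% and 90 per arm, 10% to 30% background takes power from 84% to between 71% and 47%. A baseline answer would hold it between 80% and 69%. These figures rest on assumed rates, equal background in both arms and a yes from every child already symptomatic. They show direction and rough scale, not an estimate for this trial.

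Two stronger readings go too far. That the question was asked only once is an inference from its single mention. That earlier symptoms were counted as effects of the procedure would need a counting rule, and the documents contain none.

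**What to change.** Ask about belching, bloating and flatulence as three separate yes/no items with the baseline PPP. Ask the same items on the take-home card, explicitly for the period since the procedure. Compare the arms on each symptom either as new or worse than baseline, or adjusted for the baseline answer. If worsening is to count, the card must ask about it, because two yes/no answers show only new onset. Label the comparisons as secondary and note that there are three tests.

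The cost is one extra line on the baseline form, revised card wording where needed, and slightly more parent time.

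The protocol is written in the past tense, so collection may already be complete. In that case, report that no baseline was taken, give the card's exact wording and time point, and do not interpret a null result on these symptoms as evidence that the gases do not differ.
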